5.7.3 Events

Recording of events will take place at all visits.

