7. ADVERSE REACTIONS

Side effects means anticipated reactions to treatment and typically resolve spontaneously. Anticipated events means reactions to treatment previously observed that may require medical intervention but are not serious in nature.

All adverse events that occur, starting from the time of the first treatment will be recorded in the Source Documents.

Adverse Events occurring will be captured and followed until the condition resolves, stabilizes, or is otherwise explained, or the subject is lost to follow-up. Subjects will be instructed that they may contact the Principal Investigator at any time throughout the course of the study.

The Investigator will review each event and assess its relationship to the laser treatments (not related, unlikely, possible, probable, and highly probable). The following definitions will be used for rating relationship to the laser treatments:

- Not related – The event is clearly related to other factors such as the subject’s clinical state, therapeutic interventions, or concomitant medications administered to the subject.
- Unlikely – The event was most likely produced by other factors such as the subject’s clinical state, therapeutic interventions, or a concomitant medication administered to the subject; and does not follow a known response pattern to the investigational product.
- Possible – The event follows a reasonable temporal sequence from the time of investigational product administration; and/or follows a known response pattern to the study sampling sessions; but could have been produced by other factors such as the subject’s clinical state, therapeutic interventions, or concomitant medications administered to the subject.
- Probable – The event follows a reasonable temporal sequence from the time of investigational product administration; and follows a known response pattern to the investigational product; and cannot be reasonably explained by other factors such as the subject’s clinical state, therapeutic interventions, or concomitant medications administered to the subject.
- Highly Probable – The event follows a reasonable temporal sequence from the time of investigational product administration; and follows a known response pattern to the investigational product; and cannot be reasonably explained by other factors such as the

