subject's clinical state, therapeutic interventions, or concomitant medications administered to the subject; and either occurs immediately following investigational product administration, or improves on stopping the investigational product, or reappears on repeat exposure, or there is a positive reaction at the application site.

Each adverse event reported will be graded on a 3-point severity.

The following definitions for rating severity will be used:

- Mild – easily tolerated, causing minimal discomfort, and not interfering with normal everyday activities.
- Moderate – sufficiently discomforting to interfere with normal everyday activities.
- Severe – incapacitating and/or preventing normal everyday activities.

A Serious Adverse Event is any adverse device experience that results in any of the following outcomes: death, a life-threatening adverse device experience, in-patient hospitalization or prolongation of hospitalization, a persistent or significant disability/incapacity, or a congenital anomaly/birth defect. Important medical events that may or may not result in death, be life-threatening, or require hospitalization may be considered a serious adverse device experience when, based upon appropriate medical judgment, they may jeopardize the subject or subject may require medical or surgical intervention to prevent one of the outcomes listed in this definition

If any of the above adverse events are serious as defined by the FDA Code of Federal Regulations (CFR), Title 21, special procedures will be followed. All serious adverse events will be reported within 24 hours of acknowledgment to the Medical Monitor whether or not the serious events are deemed sampling session-related. All serious event reporting will adhere to 21 CFR part 812 and the IRB will be notified accordingly.

The Medical Monitor will enter the SAE information into the database and submit a desk copy of the complete SAE report to the files.

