Adverse events, whether serious or non-serious, will be followed until the condition is resolved, stabilized, or otherwise explained, or the subject is lost to follow-up. Adverse events will be captured up to one week after a subject completes the study and where appropriate, medical tests and examinations will be performed to document the resolution of event(s). Outcomes may be classified as resolved, improved, unchanged, worse, fatal, or unknown (lost to follow-up). Following the resolution of any study-associated adverse events there will be no further adverse event reports for that subject.

PICOSURE/REVLITE

Risks to the subjects who participate in this study are the same as those for the subject undergoing infrared laser treatment. Eye injury due to direct ocular laser exposure requires the use of protective eyewear. with an optical density of 755nm- ≥ 7.0 OD, 532nm- ≥ 7 OD, 1064nm ≥ 7 OD.

Side effects of the laser treatment can include; Pain, blister, redness, swelling, bruising, pin point bleeding, crusting, itching, Some anticipated events from the treatment may include; infection, , allergic reaction, scarring, burn, hypopigmentation and hyperpigmentation.

Proper pre and post treatment standards and wound care reduces the risk of these

complications; however these conditions may or may not resolve over time.

Incomplete removal is relatively common,

Sunburn may occur if subject has unprotected exposure to ultraviolet (UV) light.

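### Section 7 ends a subject's adverse event reports once study-associated events resolve, with no time limit; read literally, this contradicts the rules for recording events throughout up to 10 sessions

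*Protocol*

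**What the plan says.** The closing paragraph of Protocol Section 7 covers follow-up of events, the capture window and outcome classes. It ends: "Following the resolution of any study-associated adverse events there will be no further adverse event reports for that subject".

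Other parts of the protocol describe continuous collection:

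- Section 5.3.2 allows up to 10 treatments, 4 to 12 weeks apart.
- The table in Section 5.4 marks an Events Assessment at screening, at treatments 1 to 10 and at the follow-up visit. Section 5.7.3 agrees: "Recording of events will take place at all visits".
- Earlier in Section 7: "All adverse events that occur, starting from the time of the first treatment will be recorded in the Source Documents".
- Two sentences before the sentence at issue: "Adverse events will be captured up to one week after a subject completes the study".
- For serious events, Section 7 has a separate rule: "All serious adverse events will be reported within 24 hours of acknowledgment to the Medical Monitor".

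Section 7 also describes the expected course of reactions. "Side effects means anticipated reactions to treatment and typically resolve spontaneously". A second group, which includes infection, scarring, burn and pigment change, is less benign: good care lowers the risk of these "complications; however these conditions may or may not resolve over time".

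**The concern.** The sentence stops reports for the subject, not for the event that has resolved, and it does not say that it applies only after the last visit. In a single-treatment study this would matter little. Here treatment is repeated, and reactions that clear between sessions are the expected course. A site that took the sentence at its word could stop reporting after an early reaction had cleared, while sessions continued.

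Safety is objective 3 in Section 1, and events are one of the outcomes that Section 15 says will be analysed. Scarring and pigment change can first appear at any session. If reporting had already stopped for that subject, such an event could be missing from what the sponsor receives and analyses.

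**Working it through.** No figure in the plan depends on this sentence, so the check is mainly one of wording.

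**1. What the sentence requires.** The trigger is resolution of study-associated events, the consequence applies to the whole subject, and no time limit is given. The trigger can be read in more than one way:

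- *Literal, single event:* the first event to resolve ends the subject's reports.
- *Literal, all events so far:* reports end once every event the subject has had to date has resolved. Without a time limit this can still happen between sessions 1 and 2.
- *Close-out:* once the study and the one-week window are over and all events have resolved, the subject's file is closed.

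**2. Each reading against the other rules.**

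| Rule | Literal readings | Close-out reading |
|---|---|---|
| Events Assessment at every visit (5.4, 5.7.3) | conflict, if later assessments are to be reported | consistent |
| All events from first treatment recorded (7) | conflict in reporting; source recording still required | consistent |
| Capture to one week after completion (7) | conflict | consistent |
| All serious events within 24 hours (7) | conflict on its face, but this rule is specific and would be expected to prevail | consistent |

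Only the close-out reading fits all the rules, but the sentence does not state the limit that this reading needs.

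**3. What is exposed.** Serious events have their own reporting rule, and source recording is a separate duty. What remains is the reporting to the sponsor of later non-serious events, including non-serious scarring and pigment change.

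**4. Illustration of scale, not an estimate.** The documents give no event rates. Assume that all 10 sessions are given, that sessions are independent, that each session carries a probability q of an event that resolves before the next one, and that a site applies the literal reading. The mean number of sessions covered by reports is (1 − (1 − q)^10)/q. The share of sessions after the stop is 1 minus that number divided by 10.

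| Assumed q | Sessions covered, of 10 | Share after the stop |
|---|---|---|
| 5% | (1 − 0.599)/0.05 = 8.0 | 20% |
| 10% | (1 − 0.349)/0.10 = 6.5 | 35% |
| 30% | (1 − 0.028)/0.30 = 3.2 | 68% |
| 50% | (1 − 0.001)/0.50 = 2.0 | 80% |
| 90% | 1.000/0.90 = 1.1 | 89% |

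The share after the stop is also the chance that a separate event, equally likely at any session, falls in the unreported period. Under the close-out reading the share is 0% at every q. The upper rows suit a trigger limited to less common events. The lower rows require short-lived side effects such as redness to count as triggering adverse events, and Section 7 does not say whether they do. Ten sessions is the maximum; with fewer, the share is smaller.

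**The case against.** The strongest reply is that no careful reader would apply the sentence literally. It uses the plural, which can mean all of a subject's events. It closes a paragraph about follow-up, the post-study window and final outcomes, so it reads as a rule for closing the file. The literal reading would cancel the capture window given two sentences earlier. A site that stopped assessing events would breach Sections 5.4 and 5.7.3 and the recording rule in Section 7. Section 9 adds sponsor training, monitoring and case report form review. One criterion for a highly probable relationship is that the event "or reappears on repeat exposure, or there is a positive reaction at the application site". This suggests that the authors expected recurrences to be assessed.

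Most of this stands. The close-out reading is plausible, and the separate duties make an outright loss less likely. The sentence concerns reports, so an unreported event could still be found in the source documents. A reader might therefore go too far in inferring that later events will be lost, or that the sponsor chose to stop safety collection during treatment. The documents support neither inference.

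The reply does not remove the defect. The plural does not supply a time limit, and the sentence before this one concerns outcome classes in general, not only the post-study period. A site is left to decide which of several conflicting instructions prevails.

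**Conclusion.** The point holds as a drafting conflict that should be corrected. The protocol has an open-ended stop on a subject's adverse event reports which, taken literally, is incompatible with its own rules for collecting events across up to 10 sessions. The consequence is conditional: a site that applied the sentence literally could leave later non-serious events unreported to the sponsor. If sites treat it as a close-out rule, the effect is nil.

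The size of any loss cannot be derived from the documents. The range in the illustration rests on assumed rates, a full course of 10 sessions and the literal reading.

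A reader might also infer that harsher settings, which cause more short-lived reactions, would lose more later events and so look safer, distorting the choice of treatment parameters under objective 1. The documents do not support that step. It needs event rates by setting, which are not given, and it needs each subject to stay on one setting, whereas Section 5.3.3 leaves parameters to the physician and fixes none per subject.

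**What to change.** Replace the sentence with wording such as:

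> Resolution of one adverse event does not end recording or reporting of later events in that subject. Events are recorded at every visit and until one week after study completion. After that, only events still ongoing are followed, until they resolve, stabilize or are otherwise explained, or contact with the subject is lost.

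The capture window and the follow-up rule are those the protocol already has, and nothing else in Section 7 needs to change. The cost is one amended sentence, which under Section 19 needs a formal amendment and written IRB approval. It requires no additional subjects, visits or procedures, and no data beyond what Sections 5.4, 5.7.3 and 7 already ask for.

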8. PROTOCOL DEVIATIONS

All requests for protocol deviations by the Investigator have to be communicated to the sponsor in writing and if accepted by the Sponsor must be approved by the IRB. If a deviation occurs, the Investigator must inform the Sponsor and IRB in writing within 10 days.

9. DATA COLLECTION AND MONITORING

The sponsor will train the site and be present at initiation of treatment. The sponsor will also monitor the site at various intervals and upon request expects to receive intermediate results by fax following each visit to evaluate treatment progress. Case Report Forms and Investigator Binders will be reviewed for current data. The sponsor will collect data at the end of the follow up period. The sponsor will list the study on clinicaltrials.gov as required by FDA regulations.

10. CONFIDENTIALITY AND DISCLOSURE OF MEDICAL INFORMATION

As part of this study the Investigator and the team at the research facility will keep records of subject participation in the study. These study records will include personal information that the subjects provide including age, sex, etc., the results of the study, information about response to treatments, photographs taken during the study and other medical information relating to participation in the study.

Under federal law the study records cannot be used or disclosed by the research Investigator for research purposes unless subjects sign the informed consent authorization.

Some or all of the test results, photographs and other information will be reported to Cynosure, Inc. the manufacturer of the test device, and consultants that are helping conduct the study. The sponsor and its consultants will analyze and evaluate these results and information and may report them to the U.S. Food and Drug Administration (the FDA) or other regulatory agencies in the United States and/or foreign countries. Study records will be assigned a code number by the study team and the subject will ordinarily not be identified by name in the study records that are sent to the Sponsor and its consultants. However, The Sponsor and its consultants will have the right to see the complete study records.

The research facility will review and use the study records only for purposes of this study. They will keep the subject identity confidential and, except for the disclosures described above, will not disclose the study records to other parties unless disclosure is required by law. Once the research facility discloses information in the study records, photographs or medical records to the Sponsor or its consultants, the information will no longer be protected by federal law. Because of the need to release information to these parties, absolute confidentiality can not be guaranteed. However, the Sponsor and its consultants will only use the information for purposes of the study and will not disclose the study records to parties other than the FDA and similar government agencies, unless disclosure is required by law. If reports or articles are written about the study, you will not be identified by name in them. The study records may be retained at the research facility indefinitely following the completion of the study.

11. DEVICE SPECIFICATIONS

The Pico Laser is manufactured by Cynosure Inc.

Device Type	Alexandrite Laser
Wavelength	755nm, 532nm, 1064nm
Pulse width	0.5 - 0.8ns
Fluence	0.5 - 6J/cm ²
Spot Size	2 –10mm

The Revlite Laser is manufactured by Conbio, a Cynosure company.

System Type	Nd:YAG
Wavelength	1064nm, 532nm
Pulse Width	5-20ns
Spot Size	1.2-8mm
Fluence	1.5 – 21 J/cm ²

12. LABELING

Sample labeling and directions for use are contained in the Operation Manual for this device.

13. CLINICAL RESEARCH CONDUCT

The study will be conducted in accordance with the protocol, International Conference on Harmonization (ICH) GCP guidelines, applicable regulations and guidelines governing clinical study conduct and ethical principles that have their origin in the Declaration of Helsinki. The investigator must ensure that the study is conducted in accordance with the provisions as stated in the FDA regulations and complies with the applicable local or regional regulatory requirements.

14. INFORMED CONSENT

During the screening, the investigator or a representative on their behalf will perform the informed consent process. At the screening, all aspects of the study will be discussed with the subject. A signed informed consent form (ICF) shall be obtained from the subject, clearly indicating his/her understanding of the study requirements, as well as the possible risks involved with study participation.

15. DATA ANALYSIS

In order to meet the objectives of our clinical study we will analyze tattoo clearance scores, PI and Subject satisfaction, and events.

16. REPORTING FOR THE STUDY

A study summary report will be generated. It will include a description of the clinical conduct of the study and results, and the statistical analysis described in the data analysis section of this protocol.

17. DISCLOSURE

The Principal Investigator, Medical Monitor, sponsor representative, and Cynosure employees have signed confidentiality agreements with the sponsor. This confidentiality agreement ensures that all information provided to the Investigator or Data Management and Statistics group dealing with the study and information obtained during the course of the study will be regarded as confidential.

18. RESPONSIBILITY OF THE INVESTIGATOR

The Investigator is responsible for ensuring that the clinical study is performed in accordance with the Declaration of Helsinki (revised version of Edinburgh, Scotland, 2000 including notes of clarification, Washington, 2002 and Tokyo, 2004) and FDA Good Clinical Practice Regulations (21 CFR parts 50, 56, and 812). Investigators will supply information to the sponsor such that the sponsor can comply with the Financial Disclosure Rules (21 CFR part 54).

19. PROCEDURE FOR AMMENDMENTS TO THE PROTOCOL

No deviations from this protocol will be permitted, except in a medical emergency, without the approval of the Sponsor. Any amendment to this study will be discussed by the Investigator and the Sponsor. If agreement is reached concerning the need for modification, this will be made in a formal amendment to the protocol. All revisions and/or amendments to the protocol must be approved in writing by the appropriate Institutional Review Board.

20. INSTITUTIONAL REVIEW BOARD

This protocol, informed consent forms, and any amendments to the protocol will be reviewed by the appropriate Institutional Review Board prior to initiation. The study will not be initiated without the approval from the Institutional Review Board.

21. TERMINATION OF STUDY

The Sponsor reserves the right to discontinue this study for administrative reasons at any time. The Investigator reserves the right to discontinue the study for safety reasons at any time in collaboration with the Sponsor.

22. STUDY RECORDS

All records and documents pertaining to the study will be maintained in appropriate permanent files as per the ICH guidelines for Essential Documents for the Conduct of a Clinical Trial and 21 CFR 11, and will be available for inspection by the Sponsor, Sponsor designee, or the Food and Drug Administration at any time.

23. CONFIDENTIALITY

After the informed consent has been signed, each subject will be entered on a screening/enrollment log, which will be kept with the study records. Once a subject is consented, a unique subject identification number will be assigned. No two subjects will have the same subject identification number. This subject identification number will identify the subject throughout the study and will be used for all source documents, and Data Collection Forms. The subject identification number will be held confidential so far as permitted by law. Investigative site staff, the Sponsor or its designee, and, under certain circumstances, the FDA and Institutional Review Board (IRB) will be able to inspect and have access to the subject identification number and the confidential data that it links to. Any publication or presentation of data will not contain any identifiable subject information.

24. DATA SECURITY

To ensure the privacy and confidentiality of data for this protocol, the data will be stored on a restricted access location on a company server. Access to the project directory containing the data will be limited to the investigators and research staff. Information about data security awareness is promoted through user training and education, supplemented by policies and procedures. Password protection will be used for all transactions that allow viewing, editing, and analysis of data, or that provide access to data fields derived from the original source documents.

## PicoRev Sample Size Rationale

The primary objectives of this study include establishing treatment parameters, assessing safety of the treatment, and comparison of the PicoSure laser to the RevLite laser. Due to the wide variety of treatment parameters to be assessed it was decided to outline up to 10 different treatment subgroups to help further identify subjects based on subject demographics, tattoo characteristics, and additional parameters that may need to be established but are not currently identified. If we assume we a treatment effect of a score of 2 on the tattoo clearance grading (0-3) which corresponds to 50% identifies a treatment effect, with a set power of 95% and a two sided significance level of 0.05, it results in a required study population of 6 subjects for each treatment subgroup. To account for subjects withdrawing or potential lost-to-follow ups due to the extended timeframe of up to 10 treatments every six weeks, it was decided to enroll up to 10 subjects in each group. With a potential of 10 total groups, it is determined that up to 100 subjects may be enrolled in the study.
